5.1. Baseline Data

Two baselines are defined. One is referred to as parent study baseline and the other one is extension study baseline.

Parent study baseline is defined as the last non-missing assessment collected before the first study treatment in the parent study. Extension study baseline is defined as the last non-missing assessment collected before the first study treatment in the extension study. Some of the information does not change and are only collected in parent studies, i.e., race, gender, and parent heights. In those cases, parent baseline data will be carried into extension study to serve as the baseline values.

For majority endpoints, including height, IGF-1 and etc., the extension study baseline values will be utilized for the analysis except for antibodies. For antibodies, the status before the first dose of TransCon will be considered as the baseline.

For annualized height, the rolling baseline will be used to calculate the annualized height velocity to make sure there is one-year gap in the calculation. In other words, from the 15-month (65 weeks) visit onwards, the baseline value used for each successive HV calculation was the patient's height at the visit 52 weeks previously, e.g. height at 13 week served as the baseline value to determine HV at the 65 week ('moving 52 weeks HV basis'). If height at visit 52 weeks previously is missing then most recent height prior to the visit will be used.

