11.3. HEIGHT MEASUREMENT

Height should be measured at each visit, preferably by the same auxologist, at approximately the same time of day using a wall-mounted stadiometer (to minimize bias and reduce variability), the accuracy of which has been verified prior to each visit using a validated metallic calibration rod.

Children < 2 years old should be measured in a recumbent position using a length board placed on a flat, stable surface such as a table. Note: despite previous height measurements being performed on a length board, once a subject is 2 years old, the subsequent measurements should be performed on a stadiometer.

For subjects \geq 2 years old, obtain the height measurement on a wall-mounted stadiometer following the general guidance below:

- The subject should not stretch prior to height determination

- The subject should be standing without shoes and socks. Thin foot covers over bare feet may be worn.
- The subject should be wearing only light clothing so that the subject's pose can be observed
- The subject's gaze should be forward and in a horizontal position (Frankfurt plane)
- The subject's heels should be placed together. If the subject has genu valgum (knock-knee), the knees must be in contact with each other and the heels as close to each other as possible
- The subject's heels, buttocks, shoulders, and occiput of the cranium should all be in contact with the stadiometer
- Upward pressure should be applied to the subject's mandibular rami (jaw)
- The subject's shoulders should be relaxed, and pressure applied to the abdomen to reduce lordosis (spine curvature)
- The counterweight head is lowered until it is in contact with the highest part of the subject's head
- The height measurement is read at the horizontal level with the counter to the nearest 0.1 cm
- The subject should step away from the stadiometer and **repeat the previous steps 2 more times**. Repeated determinations must be within 0.5 cm of each other otherwise three new measurements must be performed and recorded.

For subjects < 2 years old, obtain the height measurement on a length board following the general guidance below ([WHO, 2008](#)):

- The subject should be undressed (diaper/underwear is acceptable)
- The parent/legal guardian/caregiver or another individual should place the subject supine on the length board with the subject's head against the fixed headboard, compressing the hair

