5.3. Visit Window

The final visit of the parent trial should serve as the first visit (Visit 1) of the extension trial and data collected in the parent trial before the first study treatment will serve as baseline data for the extension trial. After Visit 1, subsequent visits will occur 5 days (± 1 day) post-dose at Week 13 (± 2 weeks) and then every 13 weeks (± 2 weeks) ongoing.

Post-baseline unscheduled visit (occurred after the date of initiation of the first dose) or end of study visit (early termination visit) will be mapped to the post-baseline scheduled visit with the closest target study day for each scheduled assessment according to Table 2. If the unscheduled visit is in the middle of two scheduled visits, map it to the later one. After mapping, if there are more than one visit in the same window, the visit closer to the target assessment day will be used. If more than one visit has the equal distance to the target day then the later one will be used, if more than one visit on the same day, use the time or the sequence number to select the later record. For listings and shift tables, all data points will be included.

Table 2. Analysis Window

VISIT	Week	Target Study Day	Study Day Window
Visit 1	Week 1	1	≤ 1
Visit 2	Week 13	90	2, 135
Visit 3	Week 26	181	136, 226
Visit 4	Week 39	272	227, 317
Visit 5	Week 52	363	318, 408
Visit 6	Week 65	454	409, 499
Visit 7	Week 78	545	500, 590
Visit 8	Week 91	636	591, 681
Visit 9	Week 104	727	682, 772
Visit x	Every 13 Weeks $13(x-1)$	$7*13*(x-1)-1$ if $x > 1$	Floor ($7*13*(x-1.5)$), Floor ($7*13*(x-0.5)$)-1

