5.4. Derived and Computed Variables

Table 3 provides the rules for derived and computed variables which have been initially identified as important for the analysis of the safety or efficacy as appropriate. It is expected that additional variables will be required. The SAP will not be amended for additional variables that are not related to the primary target or key secondary target variables. Any additional derived or computed variables will be identified and documented in the SAS programs that create the analysis files.

The birth date for each subject is collected on the eCRF. To be consistent with all the other TransCon hGH studies, the 15th day of the reported month is used to calculate the age and related scores. In such case, all the height SDS for the subjects will be calculated using 15th as the birth day. The HSDS reported in the eCRF will not be used as it is based on the actual birth date reported by the subject. FMD K&L will utilize the published SAS macro to calculate the height SDS and no independent QC is required for published SAS macro.

Table 3. Parameter Definition

Parameter	Definition
Annualized Height Velocity at visit x (HV) cm/year	$((\text{Height (Visit } x) - \text{Height (Visit } 1)) * 365) / (\text{Date (Visit } x) - \text{Date (Visit } 1))$ 
From the 15-month (65 weeks) visit onwards, the baseline value used for each successive HV calculation was the patient's height at the visit 52 weeks previously, e.g. height at 13 week served as the baseline value to determine HV at the 65 week ('moving 52 weeks HV basis'). If height at visit 52 weeks previously is missing then most recent height prior to the visit will be used.

Height Deviation Standardized Score (HSDS)	Height SDS will be derived using CDC 2000 (United States of America). A standard SAS program is published at: https://www.cdc.gov/nccdphp/dnpao/growthcharts/resources/sas.htm
Change from baseline	The value of each variable at each post-baseline time point minus the baseline score.
Normalized serum IGF-1 SDS	Proportion of subjects with IGF-1 Standard Deviation Score (SDS) of 0 to +2.0. Also derive for -2.0 to +2.0, -1.0 to +2.0.
Parents' Height SDS	$((\text{Parents Height}/M)^L - 1) / (L \times S)$ 
Where M=median, S= generalized coefficient of variation, and L= power in the Box-Cox transformation, the M, S, L values are obtained from the CDC website; Percentile Data Files with LMS Values

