9.1. Annualized HV

Annualized height velocity is calculated based on the rules stated in Section 5.4. Summary tables and listings for HV absolute values at each timepoint by each group and overall will be generated.

9.2. ΔHSDS

Height Standard Deviation Score is derived based on the rules stated in Section 5.4. Summary tables for absolute values and change from baseline at each timepoint by each group and overall will be generated. The listings will also be presented.

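### From Week 65, the SAP's fallback for a missing height 52 weeks earlier does not say which visit it counts back from and sets no interval limit, so a height velocity could cover about 13 or about 65 weeks.

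*SAP*

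**What the plan says.** SAP 5.1 gives the purpose of the moving baseline: "the rolling baseline will be used to calculate the annualized height velocity to make sure there is one-year gap in the calculation". From Week 65, each HV takes as its reference the height at the visit 52 weeks before. The SAP's example is that "height at 13 week served as the baseline value to determine HV at the 65 week". The fallback follows at once: "If height at visit 52 weeks previously is missing then most recent height prior to the visit will be used". Table 3 in SAP 5.4 repeats it without clarification.

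The Table 3 formula multiplies the height difference by 365 and divides by the days between the two visit dates. It is written out with Visit 1 as the reference.

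No other section settles the fallback. SAP 5.2 gives specific missing-data rules only for adverse event start dates. SAP 9.1 refers back to 5.4 and adds: "Summary tables and listings for HV absolute values at each timepoint by each group and overall will be generated". The protocol gives no HV derivation, and its section 14 makes the final SAP the analysis of record.

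**The concern.** The fallback sentence involves two visits: the one at which HV is being computed and the one 52 weeks earlier whose height is missing. The final words can refer to either. Counted back from the current visit, the most recent height is normally the one 13 weeks before. Counted back from the missed visit, it is normally the one 65 weeks before the current visit. Two competent programmers could therefore derive different values from the same data, and neither value has the one-year gap that the rule exists to protect.

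The current-visit reading is the one that matters. A 13-week difference scaled up to a year magnifies height measurement error and describes only the latest quarter of growth. It would sit unmarked in the same summary row as one-year velocities.

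**Working it through.** **Inputs.** SAP Table 2 target days: Visit 1 = 1, Visit 2 = 90, Visit 3 = 181, Visit 5 = 363, Visit 6 (Week 65) = 454, Visit 7 (Week 78) = 545. SAP 5.3 schedules visits "at Week 13 (± 2 weeks) and then every 13 weeks (± 2 weeks) ongoing", so the interval between two post-baseline visits can vary by 14 + 14 = 28 days. Visit 1 is taken as day 1 with no tolerance. I assume that the date in the denominator moves with the reference height.

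**Step 1: the plan's own figure.** Week 65 against Week 13: 454 - 90 = 364 days = 52 weeks. With tolerance: 336 to 392 days. The one-year gap reproduces.

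**Step 2: the fallback, when only the height 52 weeks earlier is missing.**

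| Reading | Target-day interval | With ±2-week tolerance |
|---|---|---|
| Current visit, Week 65 | 454 - 363 = 91 | 63 to 119 |
| Missed visit, Week 65 | 454 - 1 = 453 | 439 to 467 |
| Missed visit, Week 78 | 545 - 90 = 455 | 427 to 483 |

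Neither reading overlaps the planned 336 to 392 days, but the current-visit reading is much further away.

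**Step 3: measurement error.** If each visit's height has independent error with standard deviation s, the error SD of HV is √2 × s × 365 / days. Relative to a 364-day value, s cancels:

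- 91 days: 364/91 = 4.0
- 453 or 455 days: 364/453 and 364/455, both about 0.80
- 273 days (relevant to the fix): 364/273 = 1.33

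In cm/year a value of s must be assumed, because the documents give none. With s = 0.2 cm (range 0.1 to 0.3), the 95% measurement range for one subject is:

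- 91 days: 1.96 × √2 × 0.2 × 365/91 = ±2.2 cm/year (1.1 to 3.3)
- 364 days: 1.96 × √2 × 0.2 × 365/364 = ±0.56 cm/year (0.28 to 0.83)

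**Step 4: group level, current-visit reading.** Assume a between-subject SD of 2.0 cm/year, s = 0.2 cm and 5% of subjects on the fallback. The error variances are 0.284² = 0.080 at 364 days and 1.134² = 1.287 at 91 days.

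- No fallback: √(4 + 0.080) = 2.020
- With fallback: √(4 + 0.95 × 0.080 + 0.05 × 1.287) = 2.035, a rise of about 0.7%

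Varying the assumptions together (missing 1 to 10%, between-subject SD 2.5 down to 1.5, s 0.1 to 0.3) gives a rise of 0.02% to 5.4%.

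**Step 5: growth period.** If velocity changes steadily by 1 cm/year over a year, a value shifts by (182 - days/2)/364 relative to the planned one. That is 0.375 cm/year at 91 days and 0.125 in size at 273 or 455 days. At 5% affected, the group mean moves by 0.05 × 0.375 = about 0.02 cm/year under the current-visit reading. The actual change in velocity is not in the documents.

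**The case against.** The best defence is that the harmful reading is the less natural one. The missed visit is the nearest antecedent in the sentence, and a 91-day interval defeats the purpose stated just before it. The formula scales by the days elapsed, so no reading leaves a height gain unscaled. The SAP itself reports an annualized 13-week velocity at Visit 2. HV is summarized descriptively, with no test. SAP 5.3 also says that an unscheduled or end-of-study visit "will be mapped to the post-baseline scheduled visit with the closest target study day for each scheduled assessment according to Table 2", which will fill some gaps before the fallback is needed.

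All of this stands, and it limits the weight of the point. It does not remove the ambiguity: a literal programmer can take the last height before the visit being analysed. The Visit 2 comparison is also incomplete, because every subject in that row has a 13-week interval by design, whereas from Week 65 the fallback would mix intervals within a row.

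Three stronger inferences are tempting, and the documents do not support them:

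- A reader might use the outer edges of the Table 2 windows and infer a routine fallback interval as short as 409 - 408 = 1 day. SAP 5.3 states the window mapping for unscheduled and end-of-study visits. Scheduled visits carry the ±2-week tolerance, which gives 63 to 119 days.
- A reader might bound the height error by the protocol 11.3 rule: "Repeated determinations must be within 0.5 cm of each other otherwise three new measurements must be performed and recorded". That rule concerns repeat readings in one session. It says nothing about session-to-session error, and the documents do not say whether the three readings are averaged. It therefore cannot bound the visit-level SD, and only the ratios in Step 3 are free of that assumption.
- A reader might infer that the HV results as a whole are unreliable. On the illustrative assumptions above, the group-level effect is very small.

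**Conclusion.** The point holds as a minor defect of specification. From Week 65 the fallback names no anchor visit and sets no limit, and neither available reading delivers the stated one-year gap. The missed-visit reading is favoured by wording and purpose and is nearly harmless. The current-visit reading gives about a quarter of the intended interval and about four times the measurement error.

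The effect falls mainly on individual values and on the reported minimum and maximum. How many values are affected cannot be stated, because the documents give no rate of missing heights. The cm/year figures and the 0.7% rest on the assumed SDs and missing rate. The day counts rest only on Table 2, the visit tolerance and Visit 1 being day 1. HV through Week 52 uses Visit 1 as its reference, and change in height SDS uses the extension baseline, so both are unaffected.

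**What to change.** In SAP 5.1 and Table 3, replace the fallback sentence with:

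> *When no height is available from the visit 52 weeks earlier, use the available height whose actual date is closest to 52 weeks before the current visit, limited to the scheduled visit immediately before or after the missed one (nominally 65 or 39 weeks), taking the longer interval if tied. Otherwise HV at that visit is missing. Height and date are taken from the same visit.*

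Flag fallback values in the HV listing.

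At Week 65 the candidates are then Visit 1 (453 days on target, 89 from 364) and Visit 3 (454 - 181 = 273 days, 91 from 364; 245 to 301 with tolerance). The 13-week interval is excluded, and the error ratio on target days stays between about 0.8 and 1.33. The last sentence also makes explicit that the denominator moves with the reference height, which Table 3 leaves to inference.

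Simply naming the missed visit would cure the ambiguity. The fuller rule also sets a limit and stays as near to one year as the data allow. The cost is a few lines in the SAP, one listing flag and a small programming change. A few HV values may become missing; how many cannot be stated from the documents.

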5.2. Handling of Missing Data

In general, the observed data will be presented in listings. Imputed data will be used for summary analysis.

For determination of treatment-emergent adverse event (TEAE), if the start date and time of an AE are partially or completely missing, the AE will be assumed to be treatment-emergent if it cannot be definitely shown that the AE did not occur or worsen on or after the first dose in the study (worst case approach).

The following rules are used for TEAE determination where the AE has a missing start date.

If the start time of an AE is missing, but the start date is complete, an AE will only be excluded from treatment-emergent AEs if the start day is before day of first treatment or the start day is after end of study day.

If the start time and day are missing but the start month is complete, an AE will only be excluded from treatment emergent AEs if the start month is before month of first treatment or the start month is after end month of end of study month or if the stop date/time is before the start of first treatment.

If the start day and months are missing but the start year is complete, an AE will only be excluded from treatment-emergent AEs if the start year is before year of first treatment or if the start year is after end of study year or if the stop date/time is before the start of first treatment.

If the start date is completely missing, an AE will not be excluded from treatment emergent AEs unless the stop date/time is before the start of first treatment.

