11.4. PHYSICAL EXAMINATION

A physical examination should be performed to include injection site examination to assess for local tolerability. **For subjects who were treated with Genotropin in the prior TransCon hGH CT-301 trial**, Visit 1 injection site examinations to the daily hGH treatment areas should be explicitly documented so as to differentiate from any new reactions that occur during the extension trial.

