12.1.3. Reporting Procedures for All Adverse Events

At each visit, all AEs will be documented in response to a general question about the subject's well-being and whether any possible changes in well-being have occurred since the previous visit. Additionally, at each visit, site staff will review subject diary data with the subject and parent/legal guardian/caregiver, to determine if diary entries reflect any AEs. There will be no direct questioning to solicit possible AEs. AEs reported up to 14 days after the final dose of TransCon hGH will be captured. AEs, including SAEs, will be documented through the end of the subject's participation in the trial. All AEs ongoing at the completion of the study or Early Termination Visit must be followed until the event is resolved or deemed stable by the investigator. In this trial, all AEs that are considered mild and not related to investigational product will not be reported on the AE CRF. In addition, the following out-of-range laboratory values—whether or not associated with a titration of the TransCon hGH dose—will not be considered AEs unless they are associated with a clinical sign or symptom: IGF-1, IGF-1 SDS, IGFBP3, IGFBP3. In this trial, IGF-1 and IGFBP3 are pharmacodynamic markers of TransCon hGH therapy and may be used to guide an investigator's recommendation to titrate the TransCon hGH dose. Reportable AEs must be recorded on the appropriate eCRF. Reportable AEs either observed by the investigator or reported by the subject must be recorded regardless of causality.

The following attributes must be documented for each reported AE:

- Subject ID
- Description

- Onset date (if AE was present on Day 1, include whether onset was prior to or after first dose of investigational product)
- Resolution date, if applicable
- Severity
- Causality (relationship to investigational product)
- Outcome
- Action taken
- Determination of “serious” (or not)

Any ongoing AEs from the prior trial will be followed until resolution or stabilization. Any changes to the conditions documented as medical history during the trial and that meet the above AE definition should be recorded as AEs so that a complete safety profile of the investigational product is obtained. See Section 12.2.2 for additional reporting procedures for serious AEs.

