8.1. Adverse Events

AE is defined as any untoward medical occurrence in a clinical investigation subject administered a pharmaceutical product and which does not necessarily have a causal relationship with the treatment. An AE can therefore be any unfavorable and unintended sign (including

abnormal laboratory finding), symptom, or disease temporally associated with the use of a medicinal (investigational) product, whether or not related to that product. An AE can arise with any use (e.g., in combination with another drug), route of administration, formulation, or dose, including an overdose.

An AE is considered treatment emergent, i.e., Treatment Emergent Adverse Event (TEAE), is any AE that was first occurred or worsened after the first dose in this extension study and before the end of study. If the AE has any missing start date, the rules stated in Section 5.2 will be applied to determine if it is treatment-emergent.

A serious AE (SAE) is SAE is any untoward medical occurrence that:

- Results in death
- Is life-threatening
- Requires inpatient hospitalization or prolongation of an existing hospitalization
- Results in persistent or significant disability/incapacity
- Is a congenital anomaly/birth defect

Summaries of incidence rates (frequencies and percentages) of individual TEAEs by MedDRA SOC and preferred term will be prepared. Such summaries will be displayed for all TEAEs, TEAEs by maximum intensity, and TEAEs by strongest relationship to study drug. In addition, related TEAE, non-related TEAE, TEAE leading to study drug discontinuation, and serious TEAE, by SOC, the preferred term and TEAE by preferred term will be also summarized. Especially, related includes definite, probable and possible relationship. Not-related includes unlikely/remote and unrelated/not related.

Each subject will be counted only once within each preferred term. If a subject experience more than one TEAE within a preferred term, only the TEAE with the strongest relationship or the maximum intensity, as appropriate, will be included in the summaries of relationship and intensity.

Data listing of AEs, TEAE leading to study drug discontinuation, serious TEAE will also be provided.

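### The SAP's missing-time rule counts a Day 1 adverse event as treatment-emergent even when the protocol's required item records that it began before the first dose

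*SAP*

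**What the plan says.** SAP 8.1 defines the TEAE by timing: it "is any AE that was first occurred or worsened after the first dose in this extension study and before the end of study".

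SAP 5.2 then deals with incomplete onset information. Its general sentence presumes treatment emergence where timing is unclear, the test being stated in these terms: "cannot be definitely shown that the AE did not occur or worsen on or after the first dose in the study (worst case approach". Four specific rules follow. The first applies "If the start time of an AE is missing, but the start date is complete"; in that case "an AE will only be excluded from treatment-emergent AEs if the start day is before day of first treatment", or after the end-of-study day. The other three cover a missing day, a missing month and a wholly missing date. Each of those three also excludes an AE that ended before treatment began, for example "or if the stop date/time is before the start of first treatment". The missing-time rule has no such clause.

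Protocol 12.1.3 lists the attributes that must be documented for every reported AE. One is "Onset date (if AE was present on Day 1, include whether onset was prior to or after first dose of investigational product". The list contains no onset clock time. The SAP does not mention this before/after-dose item.

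**The concern.** The missing-time rule works on the calendar day alone. If an AE started on Day 1 and no time is on record, nothing else on the form can take it out of the TEAE set, including a site's statement that it began before the injection. The analysis then presumes emergence where the data show the opposite.

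Long-term safety is the primary objective, and TEAE incidence by system organ class and preferred term is its main display. The rule also treats the parent-study groups differently. Under Protocol 10.2.1, CT-301 roll-overs should take the first dose on the day of Visit 1, while CT-302 roll-overs keep their schedule and dose about two days later. A pre-dose event that starts on the Visit 1 date is therefore counted for a CT-301 child dosed that day and excluded for a CT-302 child. The SAP reports these groups separately.

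**Working it through.** The plan gives no figure to reproduce. The check is to apply the rule as written, apply the SAP 8.1 definition using the Protocol 12.1.3 item, and compare the two.

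**Step 1. Classification when the start date is complete, the time is missing and the event did not worsen later**

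| Start day | Before/after-dose item | SAP 5.2 as written | SAP 8.1 with the item |
|---|---|---|---|
| Before Day 1 | not needed | excluded | excluded |
| Day 1 | before first dose | **TEAE** | **not a TEAE** |
| Day 1 | after first dose | TEAE | TEAE |
| Day 1 | missing | TEAE | TEAE |
| Day 2 to end of study | not needed | TEAE | TEAE |

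One row differs. The worst-case presumption is kept wherever timing really is unknown.

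**Step 2. The absent stop-date/time clause.** With a complete Day 1 start date, the stop date cannot fall before Day 1. The clause would therefore help only when a stop time on Day 1 is recorded and precedes the dose. It is a small omission, but it makes this rule inconsistent with the other three.

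**Step 3. Partial dates.** The protocol item applies to any AE present on Day 1, whatever the precision of its onset date. An ongoing AE with onset known only to the month or year of first dose is also kept as a TEAE under 5.2, even if the item says that it began earlier. The same conflict arises there.

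**Step 4. How many events can reach the affected row**

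- The AE must have started on Day 1. One with an earlier complete date is excluded already.
- Genotropin is withheld on the day of Visit 1 (Protocol 9.9.1.1), so a reaction to it would normally have an earlier onset date.
- Injection-site reactions are AEs only if they limit daily activities or need medical therapy (Protocol 11.11.1).
- Mild AEs unrelated to treatment are generally not recorded (Protocol 12.1.1 and 12.1.3).
- Protocol 12.1.3 starts AE recording at the first administration, and the Schedule of Events has no AE entry at Visit 1.
- The time must be missing. If the eCRF has an onset-time field, the rule applies only when it is blank.

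The documents give no rate for what remains, so the count cannot be computed.

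**Step 5. Scale per child**

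- CT-301 is designed for about 150 children at 2:1 (Protocol 5.3). With full roll-over, an assumption, the Genotropin group is 150 / 3 = 50, and one child is 1 / 50 = 2.0 percentage points.
- At the protocol's planned 300, one child is 1 / 300 = 0.33 points. At the 400 in SAP 3.2, it is 1 / 400 = 0.25 points.

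These are upper limits. SAP 8.1 counts a child once per preferred term, so a child who later has the same term on treatment changes nothing in that row.

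**The case against.** The strongest defence is that 5.2 already has the right principle: emergence is presumed only when the contrary cannot be shown, and a recorded pre-dose onset shows it. SAP 8.1 also refers to 5.2 only for missing start dates, and here the date is complete. The approach is openly labelled worst case, the trial is descriptive with no between-group test, relatedness is tabulated separately, and all eCRF data are listed. Most of this stands and limits the consequence. It does not remove the conflict, because the specific rule names the missing-time case and limits exclusion with the word 'only'. A programmer following it would keep the event. A worst-case convention is meant for unknown timing, and here the timing may be on record.

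Two stronger readings are tempting and not supported.

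- A reader might infer that children's existing Genotropin findings become TransCon hGH TEAEs. Protocol 11.4 says that Visit 1 findings at the daily-injection sites "should be explicitly documented so as to differentiate from any new reactions that occur during the extension trial". But the SAP rule uses the start day, not presence at Visit 1, and most such findings would be dated earlier and excluded. The instruction concerns documentation of the examination, which the TEAE rule leaves intact.
- A reader might attach a rate, say 2% to 5% of children. The documents give none, and such a rate looks implausible. New onset in 2% of children on one day corresponds to 0.02 x 365 = 7.3 reportable AEs per child-year, and 5% to 0.05 x 365 = 18.3, after most mild unrelated events have been dropped.

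**Conclusion.** The point holds in a narrow form. As written, SAP 5.2 classifies one kind of event wrongly: a reportable AE that began on Day 1 before the first dose, has no recorded time, and is marked as pre-dose in the item required by Protocol 12.1.3. The result conflicts with SAP 8.1 and with the general sentence of 5.2. Children from CT-301 dosed on the day of Visit 1 are the main group exposed to it.

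The number is unknown and probably small. Each case adds at most 2 percentage points in a Genotropin group of about 50, assuming full roll-over, and at most 0.33 points among 300. The error can only overstate TEAEs, so it hides no harm. It matters only if onset time is blank or not collected, which depends on an eCRF that is not among the documents. Severity: minor.

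**What to change.** Amend SAP 5.2 as follows:

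1. For an AE with onset on the day of first dose and no start time, classify by the collected before/after-first-dose item. Count it as a TEAE if the item says after, if the item is missing, or if the event worsened after dosing.
2. Let a recorded pre-dose onset without later worsening also override the partial-date rules.
3. Add to the missing-time rule the stop-date/time exclusion that the other three rules have.

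The cost is a few lines of SAP text and one programming condition. No new data are needed, because the protocol already requires the item. The worsening condition fits existing practice, since Protocol 12.1.3 has an increase in severity or frequency recorded as a new AE. TEAE counts can only stay the same or fall slightly.
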